5.2 Exclusion Criteria

Patients are excluded from the study if any of the core criteria below and any criteria from the relevant individual modules apply.

Medical Conditions

- 1 Diagnosis of post-transplant lymphoproliferative disease, Richter's transformation, Burkitt's lymphoma, Burkitt-like lymphoma, lymphoblastic lymphoma/leukaemia, chronic lymphocytic leukaemia, small lymphocytic lymphoma.
- 2 High risk of TLS according to Howard modification of Cairo-Bishop criteria and/or the presence of bulky disease (defined as any lesion ≥ 10 cm on the screening CT scan).
- 3 Unresolved toxicity from prior anticancer therapy of CTCAE Grade ≥ 2 . Patients with Grade 2 neuropathy or Grade 2 alopecia are eligible.
- 4 Active idiopathic thrombocytopenic purpura.

- 5 Active CNS involvement by lymphoma, leptomeningeal disease, or spinal cord compression. Patients with a prior history of CNS localisation of lymphoma who received treatment are eligible provided that there is no evidence of CNS involvement at study entry as documented by cerebrospinal fluid cytology and/or brain MRI.
- 6 Known history of infection with human immunodeficiency virus.
- 7 Known serologic status reflecting active hepatitis B or C infection.
 - Patients who are anti-HBc antibody positive and who are surface antigen negative will need to have a negative PCR result before enrolment. Those who are hepatitis B surface antigen positive, or hepatitis B PCR positive will be excluded.
 - Patients who are hepatitis C antibody positive will need to have a negative PCR result before enrolment. Those who are hepatitis C PCR positive will be excluded.
- 8 Known concurrent infection with CMV.
- 9 Patients must be tested for SARS-CoV-2 and those with active infection detected using either molecular or antigen tests in accordance with local testing guidelines will be excluded. Please note: Fully recovered patients (defined as no ongoing COVID-19 symptoms, except loss of sense of smell/taste) who present persistence of positive PCR test with a negative antigen test and the presence of IgG antibodies, may be included in the study.
- 10 As judged by the Investigator:
 - Any evidence of severe or uncontrolled systemic diseases, (eg, severe hepatic impairment, interstitial lung disease [bilateral, diffuse, parenchymal lung disease]).
 - Current unstable or uncompensated respiratory or cardiac conditions.
 - Uncontrolled hypertension.
 - History of, or active, bleeding diatheses (eg, haemophilia or von Willebrand disease).
 - Uncontrolled active systemic fungal, bacterial, or other infection (defined as exhibiting ongoing signs/symptoms related to the infection and without improvement, despite appropriate antibiotics or other treatment).
- 11 Any of the following cardiac criteria at screening:
 - Patients with a history of myocarditis within one year of study entry, or heart failure New York Heart Association Functional Classification Class 3 or 4 ([Appendix J](#)).
 - Mean resting corrected QT interval (QTcF) \geq 470 msec obtained from 3 ECGs, in the absence of a cardiac pacemaker.
 - Any factors that increase the risk of QTc prolongation or risk of arrhythmic events such as congenital long QT syndrome, family history of long QT syndrome or unexplained sudden death under 40 years of age.
 - Any clinically important abnormalities in rhythm, conduction, or morphology of resting ECG (eg, complete left bundle branch block, third-degree heart block,

intermittent or persistent bundle branch block, atrioventricular block II to III, or clinically significant sinus pause).

12 History of another life-threatening malignancy \leq 2 years prior to first dose of study intervention. **The following are permitted:**

- Malignancy treated with curative intent and with no evidence of active disease present for more than 2 years before screening and considered to be at low risk of recurrence by the treating physician.
- Adequately treated lentigo malignant melanoma without current evidence of disease or adequately controlled non-melanomatous skin cancer.
- Adequately treated carcinoma in situ without current evidence of disease.

13 Any of the following procedures or any of the following conditions currently or in the 6 months prior to the first dose of study intervention:

- Coronary artery bypass graft
- Angioplasty
- Vascular stent
- Myocardial infarction
- Angina pectoris
- Haemorrhagic or thrombotic stroke, including transient ischaemic attacks or any other CNS bleeding

Prior/Concomitant Therapy

14 Treatment with any of the following:

- Radiotherapy less than 2 weeks prior to the first dose of study intervention. Radiation therapy for palliative care to focal sites is allowed.
- Any investigational agents or study drugs from a previous clinical study within \leq 14 days or 5 half-lives (whichever is shorter) prior to the first dose of study intervention, with the exception of strong CYP3A inducers or inhibitors as outlined in Section 6.5.2. Treatment with high-dose steroids for primary malignancy control is permitted, but must be discontinued at least 2 days prior to the first dose of study intervention.
- Any other chemotherapy, immunotherapy, immunosuppressant medication (other than corticosteroids) or anticancer agents within 21 days of the first dose of study intervention. A longer washout may be required for drugs with a long half-life (eg, biologics) as agreed by the Sponsor.
- Prior allogenic HSCT within 6 months from the first dose of study intervention (patients $>$ 6 months after allogenic HSCT are eligible in the absence of active graft-

versus host disease and concomitant immune-suppressive therapy). Eligible patients must have stopped immunosuppression at least 2 months prior to study entry.

- Prior cellular therapies such as CAR-T and/or autologous HSCT within 3 months prior to the first dose of study intervention.
- Major surgery (excluding placement of vascular access) \leq 21 days, or minor surgical procedures \leq 7 days, prior to the first dose of study intervention. No waiting is required following implantable port or catheter placement.
- Prescription or non-prescription drugs or other products known to be sensitive substrates of BCRP, OCT2, OAT3, OATP1B1, OATP1B3, CYP2B6, CYP2C8, CYP2C9 or CYP2D6, or reversible moderate or strong CYP3A inhibitors, which cannot be discontinued within 5 half-lives of the first dose of study intervention and withheld throughout the study until 14 days after the last dose of AZD0466 (Section 6.5.2).
- Moderate or strong mechanism-based inhibitors or inducers of CYP3A4 which cannot be discontinued within 5 half-lives plus 12 days of the drug prior to the first dose of study intervention and withheld until 14 days after the last dose of AZD0466.
- Concurrent anticoagulation therapy, including aspirin, which cannot be stopped.
- Medications with known risk of Torsades de Pointes ([Appendix H](#)) within 5 half-lives of the first dose of study intervention and continuing until 5 half-lives after the last dose of AZD0466. Some of the medications listed as a possible risk of Torsades de Pointes may be allowed at the Investigator's discretion after approval by the Study Physician when the patient has unmet medical need to continue receiving prohibited medication(s), no suitable alternative treatments are available, and the benefit-risk ratio is acceptable in the Investigator's opinion.

15 Administration of a live, attenuated vaccine within 4 weeks before first dose of study intervention.

16 Administration of inactivated vaccines or protein/RNA immunogen vaccines, including COVID-19 vaccines, within 7 days before first dose of study intervention.

Prior/Concurrent Clinical Study Experience

17 Patients with a known hypersensitivity to polyethylene glycol, pegylated products, or drugs with a similar chemical structure or class to AZD0466 or other BH3 mimetic.

Other Exclusions

18 Psychological, familial, sociological, or geographical conditions that do not permit compliance with the protocol.

19 Judgement by the Investigator or Study Physician that the patient should not participate in the study if the patient is unlikely to comply with study procedures, restrictions, and requirements.

20 Involvement in the planning and/or conduct of the study (applies to both AstraZeneca staff and/or staff at the study site).

5.3 Lifestyle Considerations

5.3.1 Meals and Dietary Restrictions

Patients should refrain from consumption of Seville oranges, grapefruit or grapefruit juice, pomelos, exotic citrus fruits, grapefruit hybrids from 14 days before the first dose of study intervention until 14 days after the last dose of study intervention.

5.3.2 Caffeine, Alcohol, and Tobacco

Patients should refrain from consumption of red wine, which has components (such as, resveratrol) that have been reported to inhibit CYP3A4. There are no caffeine or tobacco restrictions.

5.4 Screen Failures

Screen failures are defined as patients who consent to participate in the clinical study but are not subsequently entered in the study. A minimal set of screen failure information is required to ensure transparent reporting of screen failure patients to meet the Consolidated Standards of Reporting Trials publishing requirements and to respond to queries from regulatory authorities. Minimal information includes demography, screen failure details, eligibility criteria, and any SAEs.

Individuals who do not meet the criteria for participation in this study (screen failure) may be rescreened. Only one time of rescreening is allowed in the study. Rescreened patients should be assigned the same patient number as for the initial screening. However, rescreening should be documented so that its effect on study results, if any, can be assessed. Unused samples will be destroyed.

6 STUDY INTERVENTION – CORE

Study intervention is defined as any investigational intervention, marketed product, or placebo intended to be administered to or medical device utilised by a study patient according to the study protocol.

6.1 Study Intervention(s) Administered

All patients will receive treatment with the investigational product AZD0466 (Table 4). The AZD0466 drug product is provided with a custom solvent. The custom solvent is supplied to reconstitute AZD0466 drug product and subsequently dilute to lower concentrations, if needed, for clinical dosing.

Dosing details for AZD0466 administered as monotherapy or in combination with other anticancer agents are included in the relevant individual modules and associated handling instructions.

Table 4 **Investigational Product: AZD0466**

Intervention name	AZD0466
Dose formulation	AZD0466 powder for concentrate for solution for infusion supplied with Solvent for AZD0466 powder for concentrate for solution for infusion
Unit dose strength(s)	AZD0466 powder for concentrate for solution for infusion: [REDACTED] mg per vial ^a Solvent for AZD0466 powder for concentrate for solution for infusion: [REDACTED] mL per vial ^a
Dosage level(s)	Refer to the relevant individual modules. The MTD and/or RP2D dose to be decided in Module 1 Part A.
Route of administration	Intravenous
Use	Experimental
IMP or NIMP	IMP
Sourcing	AstraZeneca R&D
Packaging and labelling	AZD0466 powder for concentrate for solution for infusion will be provided in [REDACTED] mg vials. Each vial will be labelled as per country requirement. Solvent for AZD0466 powder for concentrate for solution for infusion will be provided in [REDACTED] mL vials. Each vial will be labelled as per country requirement.

^a AZD0466 powder for concentrate for solution for infusion [REDACTED] mg/vial is intended to be reconstituted with [REDACTED] mL custom solvent to produce AZD0466 concentrate for solution for infusion, [REDACTED] mg/mL. If required, AZD0466 concentrate for solution for infusion may be further diluted with custom solvent to produce AZD0466 solution for infusion for clinical dosing. Multiple vials of drug product and custom solvent may be used to achieve the required doses.

IMP = investigational medicinal product; MTD = maximum tolerated dose; NIMP = non-investigational medicinal product; RP2D = recommended Phase II dose.

6.2 Preparation/Handling/Storage/Accountability

Only patients enrolled in the study may receive study intervention and only authorised site staff may supply or administer study intervention. All study interventions must be stored in a secure, environmentally controlled, and monitored (manual or automated) area in accordance with the labelled storage conditions with access limited to the Investigator and authorised site staff.

6.2.1 AZD0466 Preparation and Administration

‘AZD0466 Powder for Concentrate for Solution for Infusion’ and ‘Solvent for AZD0466 Powder for Concentrate for Solution for Infusion’ should be prepared and administered according to the handling instructions available at the study centres.

Preparation of the dosing solutions must occur under aseptic conditions. Preparation and dosing of AZD0466 should not occur at temperatures exceeding 25°C (refer to handling instructions for allowable excursions). Administration, including 1-hour (+10 minutes) infusion time, must be completed within 3 hours of initial reconstitution (ie, addition of custom solvent to the powder).

AZD0466 doses must be administered at least 72 hours apart.

The in-use stability period is limited due to the stability of the reconstituted material. Close dialogue between the pharmacy and research staff will be required to ensure that the material is administered as quickly as possible following reconstitution, and within the in-use period/conditions stipulated.

6.2.2 Storage

The Investigator or designee must confirm appropriate temperature conditions have been maintained during transit for all study intervention received and any discrepancies are reported and resolved before use of the study intervention.

All study interventions should be kept in a secure place under appropriate storage conditions. Refer to the product label for specific storage conditions.

6.2.3 Accountability

The Investigator, institution, or the head of the medical institution (where applicable) is responsible for study intervention accountability, reconciliation, and record maintenance (ie, receipt, reconciliation, and final disposition records).

The study personnel at the investigational site will account for all drugs dispensed and for appropriate destruction of drugs to AstraZeneca. Unused drugs should be destroyed according to local guidelines, and the certificate of delivery destruction should be signed. Destruction

should not take place until approved by the responsible person at AstraZeneca. All study supplies and associated documentation will be regularly reviewed and verified by the site monitor before destruction.

Further guidance and information for the final disposition of unused study intervention is provided in the Pharmacy Manual.

6.3 Measures to Minimise Bias: Randomisation and Blinding

This is an open-label, non-randomised study; no blinding is required. If an unscheduled assessment is performed and the patient has not progressed, provided the assessment was performed within the visit window, subsequent assessments should be performed at the scheduled visits. This schedule is to be followed to minimise any unintentional bias caused by some patients being assessed at a different frequency than others.

6.3.1 Methods for Assigning Treatment Groups

Refer to the relevant individual modules for details regarding treatment group assignment.

When the study intervention is provided centrally by AstraZeneca, the IRT will provide the kit identification number to be allocated to the patient at the treatment allocation visit and subsequent treatment visits.

6.4 Study Intervention Compliance

When patients are dosed at the site, they will receive study intervention directly from the Investigator or designee, under medical supervision. The date, and time, of dose administered in the clinic will be recorded in the source documents and recorded in the eCRF. The dose of study intervention and study patient identification will be confirmed at the time of dosing by a member of the study site staff other than the person administering the study intervention.

Any changes from the dosing schedule, dose reductions and dose discontinuations should be recorded in the eCRF. The reason should also be documented.

Use of doses in excess of that specified in the protocol is considered to be an overdose. Overdose procedures to be followed in the event of overdose are described in Section [8.4](#).

6.4.1 Treatment Compliance for AZD0466

AZD0466 is administered by IV infusion and patients will receive AZD0466 directly from the Investigator or designee, under medical supervision. The date and time of dose administration will be recorded in the source documents and in the eCRF.

The Investigator or pharmacist must retain records of all study interventions administered at the site. The Study Physician will check these records to confirm compliance with the protocol administration schedule.

6.5 Concomitant Therapy

Any medication or vaccine including over-the-counter or prescription medicines, vitamins, and/or herbal supplements that the patient is receiving at the time of enrolment or receives during the study must be recorded along with:

- Reason for use
- Dates of administration including start and end dates
- Dosage information including dose and frequency

The Study Physician should be contacted if there are any questions regarding concomitant or prior therapy.

6.5.1 Permitted Concomitant Medications and Treatments

Permitted concomitant medications and treatments are listed in [Table 5](#).

Table 5 Permitted Concomitant Medications and Treatments

Supportive medication/drug class	Usage
Antiemetics (see Appendix H)	
• Permitted for the treatment of nausea and vomiting and may be administered prophylactically for recurrent events• Routine pre-medication with antiemetics for all patients is not advised
Intrathecal CNS prophylaxis	May be continued
Low-dose prednisone (≤ 10 mg) or equivalent dose of alternative	Permitted
Supportive care (including prophylactic and therapeutic anti-microbials provided they are not on the prohibited concomitant medication list [Section 6.5.2]), blood transfusions, and other medications necessary for the patient's wellbeing	May be given at the discretion of the Investigator
Erythropoietin	
• Patients already receiving erythropoietin at the time of screening for the study may continue to receive it, provided they have been receiving it for > 1 month at the time study intervention is started• Prophylactic erythropoietin should not be started before Cycle 2

Table 5 Permitted Concomitant Medications and Treatments

Supportive medication/drug class	Usage
G-CSF or GM-CSF	Primary or secondary prophylactic use of G-CSFs may be used to treat emergent neutropenia as indicated by the current ASCO guideline and according to Investigator's clinical judgement. The use of long-acting pegylated G-CSF (eg, pegfilgrastim) is not permitted during study intervention.
RANKL inhibitors and/or bisphosphonates	Permitted for the treatment of osteopenia, as recommended according to practice guidelines
Allopurinol	Mandatory for TLS prophylaxis, with dosing and schedule as per institutional guidelines
Rasburicase	Should be considered based on Appendix F and institutional guidelines
Diuretics	
 Use with care Prophylactic use should be considered only if patients have signs of volume overload
Acetaminophen (paracetamol)	Restricted to 3 grams per day or the maximum dose approved locally (if < 3 g/day) during the study
Inactivated vaccines or protein/RNA immunogen vaccines	Permitted. Note: Use of live attenuated vaccines (eg, influenza vaccine delivered as nasal spray) is prohibited
Implanted pacemaker (at study entry)	Patient is eligible at Investigator's discretion

ASCO = American Society of Clinical Oncology; CNS = central nervous system; G-CSF = granulocyte colony-stimulating factor; GM-CSF = granulocyte-macrophage colony-stimulating factor; RANKL = receptor activator of nuclear factor kappa-B ligand; TLS = tumour lysis syndrome.

Reversible strong inhibitors of CYP3A	Danoprevir, elvitegravir, indinavir, paritaprevir (ombitasvir and/or dasabuvir), posaconazole, tipranavir, and voriconazole
Reversible moderate inhibitors of CYP3A	Aprepitant, atazanavir, casopitant, cimetidine, ciprofloxacin, darunavir, dronedarone, faldaprevir, fluconazole, fluvoxamine, isavuconazole, Magnolia vine (Schisandra sphenanthera), and netupitant
Substrates of CYP2B6	Bupropion.
Substrates of CYP2C8	Repaglinide
Substrates of CYP2C9	Celecoxib, glimepiride, tolbutamide, and warfarin
Substrates of CYP2D6	Atomoxetine, desipramine, dextromethorphan, eliglustat, nebivolol, nortriptyline, perphenazine, tolterodine, venlafaxine, amitriptyline, encainide, imipramine, metoprolol, propafenone, propranolol, tramadol, and trimipramine.
Substrates of OATP1B1 and OATP1B3	Asunaprevir, atorvastatin, bosentan, cerivastatin, danoprevir, docetaxel, fexofenadine, glyburide, nateglinide, paclitaxel, pitavastatin, pravastatin, repaglinide, rosuvastatin, and simvastatin acid.
Substrates of OAT3	Adefovir, cefaclor, ceftizoxime, famotidine, furosemide, ganciclovir, methotrexate, oseltamivir carboxylate, and penicillin G.
Substrates of OCT2	Dofetilide and metformin
Substrates of BCPR	Rosuvastatin and sulfasalazine

6.6 Dose Modification and Toxicity Management

6.6.1 Starting Dose, Dose Escalation Scheme and Stopping Criteria

Refer to the relevant individual modules.

6.6.2 Dose Expansion

Refer to the relevant individual modules.

6.6.3 Definition of DLT

Refer to the relevant individual modules.

6.6.4 Definition of Maximum Tolerated Dose

Refer to the relevant individual modules.

6.6.5 Definition of DLT Evaluable Patient

Refer to the relevant individual modules.

6.6.6 Dose Escalation Committee

This study will utilise an SRC, as described in Appendix [A 5](#).

6.6.6.1 Dose Modifications

AZD0466 may be withheld and the dose reduced due to haematologic or non-haematologic toxicities. In general, no AZD0466 dose modification is required if a patient experiences a Grade 1 or Grade 2 AEs. However, AZD0466 treatment should be modified or discontinued when the AEs described in this section are observed.

AZD0466 dose modification is at the discretion of the Investigator. However, some considerations have been provided.

- For platelet and liver changes, consider Q2W ([Table 6](#)) and at second occurrence, consider triggering dose reductions ([Table 7](#)).
- For AEs other than platelet and liver-related toxicities, consider reducing the dose ([Table 7](#)).
- Dose modifications can be done in two ways, which include dose reduction and frequency change (from weekly to bi-weekly schedule). Frequency changes are not possible during ramp-up. A maximum of 3 dose modifications is acceptable, except for CTCAE Grade 3 or 4 haemorrhage and any intracranial haemorrhage or haematoma, of which only one event is allowed. See [Table 8](#), [Table 9](#), [Table 10](#), and [Table 11](#).

Table 6

Dose Frequency Changes

CCI

[figure not shown]
[figure not shown]

Table 7

Dose Reduction Modifications

CCI

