	Cycle 2 and subsequent cycles	
 Consider introducing growth factors (eg, G-CSF), evaluate patient for infection, and begin antibiotic treatment per institutional guidelines Withhold AZD0466 up to 21 days until infection is resolved, and antibiotics are no longer required (except prophylactic antibiotics), and ANC $\geq 1.0 \times 10^9/\text{L}$ 
 On first occurrence, restart AZD0466 at one lower dose (Table 7), after discussion with Study Physician On second occurrence, consider restart AZD0466 at one lower dose than the previous dose (Table 7), after discussion with Study Physician On third occurrence, restart AZD0466 at one lower dose than the previous dose (Table 7), after discussion with Study Physician unless there is no clear evidence of clinical benefit, then consider discontinuing AZD0466

Table 8 Recommended Dose Modifications for Haematologic Toxicities

Toxicity grade	Occurrence	Action
CTCAE Grade \geq 3 thrombocytopenia without the presence of significant bleeding	First occurrence	
 Withhold AZD0466 until values return to CTCAE Grade \leq 1 Restart AZD0466 at one lower dose (Table 7) if values resolve to CTCAE Grade \leq 1 within 14 days Discontinue AZD0466 if the above criteria are not met
	Second occurrence	
 Withhold AZD0466 until values return to CTCAE Grade \leq 1 Restart AZD0466 following the Q2W schedule (Table 6) if values resolve to CTCAE Grade \leq 1 within 14 days Discontinue AZD0466 if the above criteria are not met
	Third occurrence	
 Withhold AZD0466 until values return to CTCAE Grade \leq 1 Restart AZD0466 at one lower dose, maintaining the Q2W schedule (Table 6 and Table 7) if values resolve to CTCAE Grade \leq 1 within 14 days, there is clear evidence of clinical benefit and after discussion with Study Physician Discontinue AZD0466 if the above criteria are not met
	Fourth occurrence	
 Discontinue AZD0466
Presence of significant bleeding events with or without thrombocytopenia, such as: 
 Grade 3 or 4 haemorrhage Any intracranial haemorrhage or haematoma 	Any	
 Maintain platelets at $\geq 50 \times 10^9/L$ until resolution of bleeding Discontinue AZD0466

ANC = absolute neutrophil count; G-CSF = granulocyte colony-stimulating factor; Q2W = every 2 weeks.

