	Second occurrence	
Withhold AZD0466 until values return to CTCAE Grade ≤ 1 or baselineRestart AZD0466 following the Q2W schedule (Table 6) if all values resolve to baseline or Grade ≤ 1 within 14 days and after discussion with Study PhysicianDiscontinue AZD0466 if the above criteria are not met

Table 10 Dose Modification for Hepatotoxicity in Patients with Normal Baseline Liver Function

Event	Occurrence	Action with AZD0466
	Third occurrence	
 Withhold AZD0466 until values return to CTCAE Grade \leq 1 or baseline Restart AZD0466 at one lower dose than the previous dose, maintaining the Q2W schedule (Table 6 and Table 7) if all values resolve to baseline or Grade \leq 1 within 14 days, there is clear evidence of clinical benefit and after discussion with Study Physician Discontinue AZD0466 if the above criteria are not met
ALT and/or AST $\geq 3 \times$ ULN with concomitant elevation in bilirubin $\geq 2 \times$ ULN	Any occurrence	
 Discontinue AZD0466. Refer to Appendix E for process to follow in order to identify and appropriately report episodes of potential Hy's Law
ALT and/or AST $> 20 \times$ ULN	Any occurrence	
 Discontinue AZD0466

ALT = alanine aminotransferase; AST = aspartate aminotransferase; CTCAE = Common Terminology Criteria for Adverse Events; ULN = upper limit of normal; Q2W = every 2 weeks.

Table 11 Dose Modification for Hepatotoxicity in Patients with Abnormal Baseline Liver Function

Event	Occurrence	Action with AZD0466
ALT and/or AST $> 3.5 \times$ ULN and $\leq 5 \times$ ULN, without concomitant elevation in bilirubin	First occurrence	
 Withhold AZD0466 until values return to CTCAE Grade \leq 1 or baseline Restart AZD0466 at same dose level if all values resolve to baseline or CTCAE Grade \leq 1 within 14 days Discontinue AZD0466 if the above criteria are not met
	Second occurrence	
 Withhold AZD0466 until values return to CTCAE Grade \leq 1 or baseline Restart AZD0466 at one lower dose (Table 7) if all values resolve to baseline or Grade \leq 1 within 14 days Discontinue AZD0466 if the above criteria are not met

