10.9.3 Populations for Analyses

The analysis populations for Module 1 Part A and Part B are summarised in [Table 26](#).

Table 26 Module 1 Part A and Part B Analysis Populations

Analysis population	Description
Safety	All patients who received at least 1 dose of AZD0466
Intent-to-treat	All patients who received at least 1 dose of AZD0466
Evaluable for Response	All patients who have received at least 2 doses of AZD0466 at the target dose level in Cycle 1
DLT Evaluable	Patients enrolled in dose escalation who have received at least 2 doses of AZD0466 at the target dose level (67% of target doses from Day 8 to Day 22 in Cycle 1) and have completed the safety follow-up through the DLT evaluation period or have experienced a DLT
Pharmacokinetics	Dosed patients with reportable plasma concentrations and no important AEs or protocol deviations that may impact PK

AE = adverse event; DLT = dose-limiting toxicity; PK = pharmacokinetics.

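### Section 6.6.6.1 and Tables 8, 10 and 11 order the 2-weekly schedule and dose reduction differently after platelet or liver toxicity, and no explicit precedence is stated

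*Protocol*

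**What the plan says.** Protocol Section 6.6.6.1 gives one sequence for platelet and liver changes: "For platelet and liver changes, consider Q2W" "and at second occurrence, consider triggering dose reductions". The same section says that "AZD0466 dose modification is at the discretion of the Investigator", that "Frequency changes are not possible during ramp-up", and refers the reader to Tables 8 to 11.

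Table 8, for Grade ≥ 3 thrombocytopenia without significant bleeding, says at the first occurrence "Restart AZD0466 at one lower dose (Table 7) if values resolve to CTCAE Grade" ≤ 1 within 14 days, and at the second "Restart AZD0466 following the Q2W schedule (Table 6) if values resolve to CTCAE Grade" ≤ 1 within 14 days. Table 10, for ALT/AST > 8 to ≤ 20 × ULN with normal baseline, says at the first occurrence "Restart AZD0466 at one lower dose (Table 7) if all values resolve to baseline or Grade" ≤ 1 within 14 days, and moves to Q2W at the second.

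Other sections bear on the same step. The text of 6.6.6.2 describes a restart one dose lower. Section 6.6.7 (resumption) points to Section 6.6.6 and Tables 8 to 11. Section 10.6.6.7 sends Module 1 back to 6.6.6.1. Section 10.6.6.2 lets a 2-weekly schedule be considered in Part B for liver or haematologic toxicity.

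Table 26 defines the response-evaluable set as "All patients who have received at least 2 doses of AZD0466 at the target dose level in Cycle 1"; SAP Table 6 adds measurable disease at baseline. Section 10.6.6.5 puts the same 2-dose condition on the DLT-evaluable patient, unless a DLT has occurred.

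**The concern.** Two current instructions on one event disagree about what comes first. Thrombocytopenia and hepatotoxicity are two of the three important potential risks in Protocol Table 1, and Section 4.5 calls thrombocytopenia an on-target effect, so the instruction is one that sites can be expected to consult. Two sites that both follow the protocol can deliver different regimens after the same toxicity.

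The planned outputs would not show this clearly. SAP Section 5.6.1.2 summarises reductions, interruptions and delays, with no category for a change of schedule.

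There is also a possible link to the analysis sets. The DLT summary and the primary ORR analysis use sets that count target-level doses, so the path chosen in Cycle 1 may decide whether a patient is in them.

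**Working it through.** **Step 1: the sequences side by side** (rows that allow a restart).

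| Source | First occurrence | Second | Third |
|---|---|---|---|
| Section 6.6.6.1, platelet and liver | Q2W | dose reduction | not given |
| Table 8, Grade ≥ 3 thrombocytopenia, no significant bleeding | lower dose | Q2W | lower dose, on Q2W |
| Table 10, > 8 to ≤ 20 × ULN | lower dose | Q2W | lower dose, on Q2W |
| Table 11, > 5 to ≤ 8 × ULN | lower dose | Q2W | lower dose, on Q2W |
| Table 10, > 5 to ≤ 8 × ULN | same dose | lower dose | Q2W |
| Table 11, > 3.5 to ≤ 5 × ULN | same dose | lower dose | Q2W |
| Table 11, > 8 to ≤ 20 × ULN | lower dose and Q2W together | further lower dose, on Q2W | discontinue |

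Three of the six table rows directly reverse 6.6.6.1. Two begin with an unmodified restart and then put the lower dose before Q2W. One applies both at once. In none is Q2W alone the first modification.

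**Step 2: the evaluability threshold.** Section 10.6.6.1 plans 3 target-level doses in Cycle 1, on Days 8, 15 and 22. Two of three is 2/3 = 66.7%, which reproduces the 67% in Section 10.6.6.5.

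**Step 3: target-level doses in Cycle 1 after a first event.** Assumptions: Q2W keeps the target dose (Tables 6 and 7 are redacted); a reduced dose does not count as target level (not defined); modification applies within Cycle 1; the event is not a DLT. For platelets under Section 10.6.6.3, that last condition means no Grade ≥ 2 bleeding or platelet transfusion with Grade 3, and no Grade 4 lasting more than 7 days.

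| Onset and recovery | Q2W | Lower dose | Same dose |
|---|---|---|---|
| After Day 8 dose, before Day 15 dose; recovered by Day 22 | 2 (Days 8, 22) | 1 (Day 8) | 2 or 3 |
| Same onset; recovered after Day 22 | 1 | 1 | 1 |
| After Day 15 dose, before Day 22 dose | 2 | 2 | 2 or 3 |
| After Day 22 dose | 3 | 3 | 3 |

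Only the first line crosses the threshold: 2/3 = 67% against 1/3 = 33%. During ramp-up Q2W is unavailable, so the contrast does not arise. In the same-dose rows of Tables 10 and 11, first-occurrence membership matches the Q2W path.

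**Step 4: illustrative size.** Cohort sizes and the DLT target are redacted, and no event rate is given, so these figures are assumptions.
- Part A: one non-DLT patient leaving turns 1/3 into 1/2, or 1/6 into 1/5, until replaced.
- Part B, assumed ORR 30%, one to three non-responders leaving: with N = 20, 6/19 = 31.6% to 6/17 = 35.3%; with N = 40, 12/39 = 30.8% to 12/37 = 32.4%.
- One responder leaving instead: 5/19 = 26.3% or 11/39 = 28.2%.

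**The case against.** The best defence is that 6.6.6.1 is advisory. It leaves modification to the investigator, uses the language of consideration, and Table 8 is headed as recommended. Sites could differ even if the texts matched. Moreover, the disputed step is a restart, and the resumption section names Tables 8 to 11, while 6.6.6.2 agrees with Table 8 on a lower dose.

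Much of this stands. The documents do lean towards the tables, and not all variation between sites could be blamed on the conflict. But a lean is not a rule. Section 6.6.7 points to the whole of 6.6.6, which contains the competing bullet; 10.6.6.7 sends Module 1 to that bullet; and 10.6.6.2 keeps Q2W open. Discretion does not tell a site which of two written sequences is the default.

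The objection to the analysis-set effect is also partly right. Section 6.6.6.2 speaks of withholding in later cycles; read literally, that removes the Cycle 1 platelet case. Against this, the thrombocytopenia rows run by occurrence, not by cycle, and the liver tables carry no such limit. Part A replaces non-evaluable patients. The ITT sensitivity analysis in SAP Section 5.2.1.3 would show the effect on ORR, though it leaves the primary analysis unchanged. PFS, OS and safety use the ITT or Safety sets and are untouched.

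**Conclusion.** The contradiction in sequence is real, current and unresolved, and reconciling it is justified on that ground alone. Its effect on the analysis sets is a conditional note: 1 against 2 target-level doses, for a first non-DLT event between the Day 8 and Day 15 doses that recovers by Day 22, under the assumptions in the working.

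Three stronger readings are tempting and are not supported.
- A reader might infer that every platelet and liver row reverses 6.6.6.1. Three rows do; the two lowest ALT/AST bands start with the same dose, and one row of Table 11 combines both steps.
- A reader might infer that the same event contributes opposite results to the MTD or ORR. The contrast is included against excluded (and replaced in Part A); no DLT becomes a non-DLT, and no responder becomes a non-responder.
- A reader might infer that this path will be common. Table 1 lists potential risks from nonclinical data and gives no rate.

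Which sequence is clinically right is outside this review.

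**What to change.** Reconcile Section 6.6.6.1 with Sections 6.6.6.2 and 10.6.6.2 and with Tables 8, 10 and 11, or state explicitly which text prevails. The sponsor's clinical team chooses the sequence; none is proposed here. Then state in Section 10.6.6.5 and Table 26, and in SAP Table 6 and Section 11.1.9.1 where the definitions are repeated, whether doses given at a reduced level or on the 2-weekly schedule count towards the 2 target-level doses. The cost is wording in the next amendment and a matching SAP edit, with no extra patients or procedures.
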